11.3.2. Reporting

To ensure subject safety, every SAE, regardless of suspected causality, occurring after the subject has signed the informed consent form (ICF) and until (at least) the Follow-up Visit or 30 days after the subject has stopped study treatment (whichever comes later) must be reported to the Sponsor or designee within 24 hours of learning of its occurrence. Any SAEs experienced after this period of at least 30 days should only be reported to the Sponsor, or designee, if the Investigator suspects a causal relationship to the study medication. Recurrent episodes, complications, or progression of the initial SAE must be reported as the follow-up to the original episode within 24 hours of the Investigator receiving the follow-up information. An SAE occurring at a different time interval or otherwise considered completely unrelated to a previously reported one should be reported separately as a new event. Serious AE collection begins after the subject has signed the ICF. If a subject experiences an SAE after signing the ICF, but prior to receiving study medication, the event will **not** be collected unless the Investigator feels the event may have been caused by a protocol procedure. Previously planned (prior to signing the ICF) surgeries should not be reported as SAEs unless the underlying medical condition worsens over the course of the study.

Information about all SAEs is collected and recorded on the Serious Adverse Event Report Form. The Investigator must assess and record the relationship of each SAE to each specific study medication (if there is more than 1), complete the SAE Report Form in English, and send the completed, signed form by fax within 24 hours to the Sponsor (or designee). The investigator must assess if there is a Reasonable possibility that the SAE is related to the study treatment: no (unrelated), yes (related).

SAEs related to unblinded comparator drugs or concomitant medications/drug delivery systems are reported directly to the manufacturers of those drugs/devices in accordance with the package insert.

The telephone and facsimile number of the Sponsor's contact persons, specific to the study, are listed in the investigator folder provided to each site. The original copy of the SAE Report Form and the fax confirmation sheet must be kept with the case report form documentation at the study site.

Follow-up information is sent to the same person to whom the original SAE Report Form was sent, using a new SAE Report Form stating that this is a follow-up to the previously reported SAE and giving the date of the original report. Each re-occurrence, complication, or progression of the original event should be reported as a follow-up to that event regardless of when it occurs. The follow-up information should describe whether the event has resolved or continues, if and how it was treated, and whether the subject continued or withdrew from study participation or if study medication was interrupted or discontinued.

If the SAE is not previously documented in the Investigator's Brochure for the study medication (new occurrence) and is thought to be related to the Sponsor's study drug, a Sponsor's associate may urgently require further information from the Investigator for reporting to Health Authorities.

The Sponsor may need to issue an Investigator Notification (IN) to inform all Investigators involved in any study with the same drug that this SAE has been reported. Suspected Unexpected Serious Adverse Reactions (SUSARs) will be collected and reported to the competent authorities and relevant ethics committees in accordance with Directive 2001/20/EC or as per national regulatory requirements in participating countries. If the study is open-label, no special unblinding procedures are needed for exceptional circumstances or medical emergencies.

11.4. Emergency Unblinding of Treatment Assignment

Not applicable, study is open label.

11.5. Pregnancy

Pregnancy, in and of itself, is not regarded as an AE, unless there is suspicion that study medication may have interfered with the effectiveness of a contraceptive medication or method. The procedures that will be followed based on whether a pregnancy is confirmed by a positive serum or urine test result are listed below:

- Investigator and subject must notify each other immediately
- Investigator must notify the Sponsor immediately
- Study medication must be discontinued immediately
- Subject must be withdrawn from the study
- Perform the required End-of-treatment Visit evaluations
- Investigator must complete and submit the Pregnancy Initial and Follow-up report forms to the Sponsor

- A serum pregnancy test must be performed to confirm the urine test result. (The serum test should be performed at the investigative site to ensure the test will be performed promptly and the result available immediately for review.)

If a negative serum test does not confirm the urine test result, then:

- The Investigator will use his/her expert judgment, based on an assessment of the potential benefit/risk to the subject, to determine if it is in the subject's best interest to resume study drug and continue participation in the study.

To ensure subject safety, each pregnancy in a subject during maternal or paternal exposures to study medication must be reported within 24 hours of learning of its occurrence. Data on fetal outcome and breast-feeding are collected for regulatory reporting and drug safety evaluation. The pregnancy should be followed-up to determine outcome, including spontaneous or voluntary termination, details of the birth, and the presence or absence of any birth defects, congenital abnormalities, or maternal and/or newborn complications by following until the first well-baby visit. Pregnancy should be recorded on a Clinical Study Pregnancy Form and reported by the Investigator to the Sponsor. Pregnancy follow-up should be recorded on the same form and should include an assessment of the possible relationship to the Sponsor's study medication of any pregnancy outcome and follow-up to the first well-baby visit. **Any SAE experienced during pregnancy must be reported on the SAE Report Form and needs to be reported to Incyte Corporation.**

11.6. Warnings and Precautions

No evidence available at the time of the approval of this study protocol indicated that special warnings or precautions were appropriate, other than those noted in the provided Investigator Brochure. Additional safety information collected between IB updates will be communicated in the form of Investigator Notifications (INs). This information will be included in the subject informed consent and should be discussed with the subject during the study as needed.

11.7. Data Safety Monitoring

11.7.1. Data Monitoring Committee

An independent Data Monitoring Committee (DMC) will be formed. It will consist of qualified individuals who are not involved with the conduct of the study. The establishment, composition, roles, duties and responsibilities of the DMC will be addressed in an approved DMC charter. The timing of data review by the DMC will be specified in the charter, but at a minimum, will include review of safety data with an emphasis on events of thrombocytopenia and hemorrhage at least 28 days after 20 subjects have been enrolled into the study and 28 days after 40 subjects have been enrolled into the study.

11.7.2. Reporting of Grade 4 Thrombocytopenia Events and > Grade 2 Hemorrhage Events During the Study

The study is designed to assess the efficacy and safety of ruxolitinib in a myelofibrosis patient population with platelet counts of 50 to 100 x 10⁹/L. As these patients are potentially at higher risk for greater degrees of thrombocytopenia and bleeding, events of Grade 4 thrombocytopenia

and > Grade 2 hemorrhage will be monitored on an ongoing basis. Investigators will be required to notify the sponsor via FAX of any Grade 4 thrombocytopenia event and any Grade 3 or Grade 4 event of hemorrhage, regardless of suspected causality. The notification must occur within 24 hours of the time the site first becomes aware of the event. All such events occurring after a subject has signed informed consent and received at least one dose of study drug up to the follow-up visit (or at least 30 days after the last dose of study drug is taken) must be reported. The notification form (supplied by sponsor) will require the site to provide information regarding dosing history, platelet count, event description and any other information pertinent to the event.

11.7.3. Safety Reviews

As ruxolitinib has been studied extensively in the myelofibrosis population in Phase II and III trials, its safety profile is generally well characterized in patients with platelet counts above $100 \times 10^9/L$. Because this trial is designed to assess the efficacy and safety of ruxolitinib in a myelofibrosis patient population with platelet counts of 50 to $100 \times 10^9/L$, there will be a review of safety with an emphasis on events of thrombocytopenia and hemorrhage at regularly scheduled intervals corresponding to when:

1. 20 patients have been enrolled
2. 40 patients have been enrolled

Additional safety reviews as deemed necessary by the DMC or the sponsor may be conducted at any time

11.7.3.1. Review After Enrollment of 20th Subject

When the 20th patient is enrolled, additional screening of subjects will be paused for at least 28 days and up to approximately 42 days. Subjects in screening at that time will be allowed to enroll if they are found to be eligible. During this period, enrolled subjects will be allowed to continue on study per protocol. At least twenty eight days from the enrollment of the 20th subject, safety data will be assessed by the DMC and the sponsor. Subjects will be analyzed if they have completed at least 28 days on the study or have discontinued the study due to Grade 4 thrombocytopenia or > Grade 2 hemorrhage. If fewer than 33% of the subjects had an event of Grade 4 thrombocytopenia and fewer than 10% of these subjects had an event of > Grade 2 hemorrhage, the study may resume enrollment without amendment. If these criteria are not met, or other safety concerns are revealed, a recommendation will be made for one of the following actions:

1. Stop the trial
2. Recommend amendments and suspend enrollment until the amendments can be implemented
3. Continue enrollment with a new dosing cap (with subsequent amendment of the protocol)
4. Continue the trial without amendment (must be agreed upon by both the Sponsor and the DSMC)

11.7.3.2. Review After Enrollment of 40th Subject

At least 28 days from the enrollment of the 40th subject, safety data will be assessed by the DMC and the sponsor. Since the first dose escalation opportunity in the study is at Day 28 and the starting dose for all subjects of 5 mg bid will have been adequately assessed for safety at the first safety review after the enrollment of 20 patients, screening will not be suspended following enrollment of the 40th subject. If safety of the 5 mg bid dose is not clear from this first data review, the DMC and sponsor may mandate a hold on screening at the review that occurs with enrollment of the 40th subject. Subjects will be analyzed if they have completed at least 28 days on the study or discontinued due to grade 4 thrombocytopenia or > Grade 2 hemorrhage. If 33% or fewer of the subjects had an event of Grade 4 thrombocytopenia and 10% or fewer of these subjects had an event of > Grade 2 hemorrhage, the study may resume enrollment without amendment. If these criteria are not met, or other safety concerns are revealed, a recommendation will be made for one of the following actions:

1. Stop the trial
2. Recommend amendments and suspend enrollment until the amendments can be implemented
3. Continue enrollment with a new dosing cap (with subsequent amendment of the protocol)
4. Continue the trial without amendment (must be agreed upon by both the Sponsor and the DSMC)

The DMC and the sponsor will also specifically evaluate the event rates for Grade 4 thrombocytopenia and > Grade 2 hemorrhage in subjects from the initial cohort of 20 subjects who have had longer follow-up and opportunities for dose escalation.

11.7.4. Continuous Safety Monitoring

Events of Grade 4 thrombocytopenia and > Grade 2 hemorrhage will be monitored continuously. Subjects will be analyzed if they have completed at least 28 days on the study or discontinued due to Grade 4 thrombocytopenia or > Grade 2 hemorrhage. If at any time > 33% of these subjects have an event of Grade 4 thrombocytopenia, or > than 10% of the subjects have an event of > Grade 2 hemorrhage, the sponsor will temporarily hold further screening and seek consultation with the DMC. A recommendation will be made for one of the following actions:

1. Stop the trial
2. Recommend amendments and suspend enrollment until the amendments can be implemented
3. Continue enrollment with a new dosing cap (with subsequent amendment of the protocol)
4. Continue the trial without amendment (must be agreed upon by both the Sponsor and the DMC).

11.8. Product Complaints

Incyte collects product complaints on study medications and drug delivery systems used in clinical studies in order to ensure the safety of study participants, to monitor quality, and to facilitate process and product improvements.

All product complaints associated with material packaged, labeled, and released by Incyte or its designee will be reported.

The Investigator or his/her designee is responsible for handling the following aspects of the product complaint process in accordance with the instructions provided for this study:

- Recording a complete description of the product complaint reported and any associated AEs using the study-specific complaint forms provided for this purpose
- Faxing the completed product complaint form within 24 hours to Incyte or its designee.

If the Investigator is asked to return the product for investigation, he/she will return a copy of the product complaint form with the product.

12. STATISTICS

12.1. Study Population

Intent-to-treat (ITT): includes all subjects enrolled in the study.

Per-protocol (PP): includes subjects who are considered to be sufficiently compliant with the protocol.

Safety Evaluable: includes subjects who received at least 1 dose of study drug.

12.2. Statistical Analyses

12.2.1. Primary Analyses

Co-Primary Endpoints:

- Correlation of % change in spleen volume at Week 24 compared to baseline versus final titrated dose.
- Correlation of % change in Total Symptom Score as measured by the modified MFSAF v2.0 diary at Week 24 compared to baseline versus final titrated dose.

The null hypothesis is that the correlation between percent change in spleen volume or total symptom score and final titrated dose is zero. The test will be based on the t test for a product-moment correlation coefficient:

$$t = r_{xy} \sqrt{(n - 2) / (1 - r_{xy}^2)}$$

(Cohen 1988, Formula 3.1.1)

A two-sided alpha of 5% will be used. With a sample size of 150, the critical correlation that is needed to reject H_0 is 0.16. If the absolute value of the observed correlation is 0.16 or higher, H_0 will be rejected. In order to keep the overall alpha at 5%, a sequential testing procedure will be used: First we will test the correlation with % change in spleen volume, and only if the null hypothesis of no correlation can be rejected will we continue to test the correlation with % change in Total Symptom Score.

Safety Endpoints:

Safety and tolerability will be assessed by monitoring the frequency, duration and severity of adverse events, performing physical examinations, collecting vital signs, collecting laboratory data for hematology, serum chemistry, coagulation parameters, and lipid panel through Week 156.

Change in platelet count from baseline to each visit where the variables are measured will be tabulated with summary statistics.

Proportion of subjects with new onset of Grade 4 thrombocytopenia events, and proportion of subjects with new onset of Grade 2 or higher hemorrhage, as measured by CTCAE will be tabulated with summary statistics. The hazard functions of time to onset of the above two safety measures will be estimated using life table method.

Adverse events will be tabulated by the Medical Dictionary for Regulatory Activities (MedDRA[®]) preferred term and by system organ class. Severity of AEs will be based on the CTCAE scale as indicated in [Section 11.1.1](#).

The subset of AEs that are considered by the Investigator to be related to study drug will be considered to be treatment-related AEs. If the Investigator does not specify the relationship of the AE to study drug, the AE will be considered to be treatment-related. The incidence of AEs and treatment-related AEs will be tabulated.

Clinical Laboratory Tests

The clinical laboratory data will be analyzed using summary statistics (eg, means and frequencies), and no formal statistical comparisons among the treatments are planned.

Vital Signs

Descriptive statistics and mean change from baseline will be determined for vital signs (body temperature, respiratory rate, blood pressure and heart rate) at each assessment time. Vital sign results will be reviewed for clinically notable abnormalities according to the criteria shown below; subjects exhibiting clinically notable vital sign abnormalities will be listed.

| Parameter | High Threshold | Low Threshold |
|--------------------------|-----------------------|----------------------|
| Systolic blood pressure | > 160 mm Hg | < 85 mm Hg |
| Diastolic blood pressure | > 100 mm Hg | < 50 mm Hg |
| Respiratory Rate | > 24 per minute | < 8 per minute |
| Heart rate | > 100 bpm | < 45 bpm |

[figure not shown]
Note: mm Hg = millimeters of mercury; bpm = beats per minute.

12.2.2. Secondary Analyses

Secondary Endpoints

- Percent change in spleen volume at Week 24 compared to Baseline
- Percent change in Total Symptom Score as measured by the modified MFSAF v2.0 diary at Week 24 compared to baseline
- Proportion of subjects with $\geq 35\%$ reduction in spleen volume at Week 24 compared to baseline
- Proportion of subjects with $\geq 10\%$ reduction in spleen volume at Week 24 compared to baseline
- Proportion of subjects with $\geq 50\%$ improvement in total symptom score as measured by the modified MFSAF v2.0 diary at Week 24 compared to baseline

Long-term efficacy of ruxolitinib will be assessed by monitoring change and percent change in spleen length, as measured by palpation, and change in PGIC score from baseline to each visit where the variables are measured through Week 156. The percent change in spleen volume at Week 24 compared to baseline, the percent change in Total Symptom Score as measured by the modified MFSAF v2.0 diary at Week 24 compared to baseline, the proportion of subjects with $\geq 35\%$ reduction in spleen volume at Week 24 compared to baseline, proportion of subjects with $\geq 10\%$ reduction in spleen volume at Week 24 compared to baseline, and the proportion of subjects with $\geq 50\%$ improvement in total symptom score as measured by the modified MFSAF v2.0 diary at Week 24 compared to baseline will be tabulated with summary statistics. Change and percentage change in spleen length from baseline as measured by palpation at each visit where the parameter is assessed through Week 156 will be tabulated with summary statistics. The data will be summarized as one group and by the final titrated dose. The final titrated dose will be based on dosing data up to Week 24.

12.3. Interim Analysis

Interim data review focused on thrombocytopenia and hemorrhage events will occur as described in [Section 11.7](#) Data Safety Monitoring.

12.4. Selection of Sample Size

Approximately 150 subjects will be enrolled. Using an alpha of 5% (two-sided), this sample size gives a power of 96% to reject the null hypothesis of no dose-effect correlation if the true correlation is 0.30. The power is 87% if the true correlation is 0.25, and the power is 69% if the true correlation is 0.20. These calculations are based on ([Cohen 1988](#), Formula 12.3.4).

In addition, the mean percent change of spleen volume measured by MRI, and mean percent change in Total Symptom Score from baseline to Week 24 will each be estimated with a 95% confidence interval. With 150 subjects, the half-length of the 95% confidence interval of the spleen volume change from baseline to Week 24 is about 3%. This is based on the Phase III study (INCB 18424-351), where the standard deviation of the percent change of spleen volume from baseline to Week 24 was 19%.

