4.1.5. Interim Analysis Data from Study INCB 18424-258

In Study INCB 18424-258, subjects with platelet counts of 50 to $100 \times 10^9/L$ were enrolled to begin administration of ruxolitinib at 5 mg BID, which is a dose that represents a conservatively low starting dose, that data from earlier studies suggested should have a limited impact on platelet count. Subjects could then titrate their dose to an appropriate dose that offers benefit (eg, symptomatic and/or spleen size improvements) with cautious monitoring to avoid levels of thrombocytopenia associated with higher risk of spontaneous hemorrhage. Ruxolitinib administration was interrupted for a platelet count below $25 \times 10^9/L$ or for Grade 2 or higher hemorrhage events.

The study is currently in the enrollment phase; however, an interim analysis was conducted based on a data cutoff when it was expected that at least 20 subjects would have completed 24 weeks of treatment. At the time of the interim analysis, a total of 50 subjects had enrolled in the study. Of the 50 subjects enrolled, 33 (66.0%) subjects completed the Week 24 visit,

8 (16.0%) discontinued prior to Week 24, and 9 (18.0%) subjects remained on study and had not yet completed their Week 24 visit.

Most subjects were titrated to a ruxolitinib dose of 10 mg BID or higher by Week 24 and 20.0% of subjects had a $\geq 35\%$ reduction in spleen volume at Week 24. This is consistent with the proportion of subjects in Study INCB 18424-351 who had a $\geq 35\%$ reduction in spleen volume at Week 24 who initiated treatment at a dose of 15 mg BID (21.8%), and substantially higher than that observed for placebo-treated subjects in Study INCB 18424-351 (1.7%). In addition, Mesa et al (2011) has shown that a spleen volume reduction of $\geq 10\%$ is associated with meaningful improvements in symptoms and other measures of patient-perceived benefit (Patient Global Impression of Change [PGIC] and Myelofibrosis Symptom Assessment Form [MFSAF v2.0]).

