### 4.3. Sample Size Considerations

Approximately 150 subjects will be enrolled in order to assess (on the efficacy side) the dose-effect correlation (between percent changes from baseline in spleen volume/total symptom score at Week 24 and final titrated dose level). Using an alpha of 5% (2-sided), this sample size gives a power of 96% to reject the null hypothesis of no dose-effect correlation if the true correlation is 0.30. The power is 87% if the true correlation is 0.25, and the power is 69% if the true correlation is 0.20. These calculations are based on [Cohen 1988](#), Formula 12.3.4. SAS procedure POWER is used and the power curves are displayed in Figure 1.

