**Figure 1: Power and Sample Size Curves for 3 Alternative Hypotheses on the Level of Dose-Effect Correlation**

It is noted that the above sample size calculation is based on the rationale that the first primary endpoint (correlation between percent change from baseline in spleen volume at Week 24 by the final titrated dose) is powered following the procedure of the sequential test used for this study (see [Section 5.4.2](#)). At the given sample size, power can also be assessed for the second co-primary endpoint (correlation between percent change from baseline in total symptom score at Week 24 by the final titrated dose).

In addition, the mean percent change from baseline in spleen volume measured by MRI, and mean percent change from baseline in total symptom score at Week 24 will each be estimated with a 95% confidence interval. With 150 subjects, the half-length of the 95% confidence

interval of the change from baseline in spleen volume at Week 24 is approximately 3%. This is based on the Phase 3 study (INCB 18424-351), where the standard deviation of the percent change from baseline in spleen volume at Week 24 was 19%.

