## 7. EFFICACY ANALYSES

### 7.1. Primary Efficacy Endpoints

For the co-primary endpoints (correlation of percent change from baseline in spleen volume at Week 24 versus final titrated dose, and correlation of percent change from baseline in total symptom score at Week 24 versus final titrated dose), the following t-test will be used generate the p-values:

$$T = r \times \sqrt{\frac{n-2}{1-r^2}} \sim t_{n-2} | H_0$$

where  $r$  is the product-moment (Pearson) correlation coefficient,  $n$  is the sample size of paired observations, and  $\sim t_{n-2} | H_0$  means the test statistic will follow a  $t$ -distribution with  $n-2$  degrees of freedom under the null hypothesis.

In addition, correlation estimate and the corresponding approximate 95% confidence intervals will be calculated by using the Fisher's  $r$ -to- $z$  transformation. The following SAS codes will be used to generate the all these statistics:

```
ODS OUTPUT FisherPearsonCorr=correst PearsonCorr=pval;  
PROC CORR FISHER PEARSON;  
VAR X Y;  
RUN; ***CORREST has point estimate and CI from Fisher z-transformation, and  
PVAL has p-value and the raw Pearson correlation coefficient ***;
```

The analysis will be generated for the ITT population. The same analysis will be repeated by using The PP population as a sensitivity analysis (Sensitivity Analysis 1).

An additional sensitivity analysis may be generated in dealing with missing data by using multiple imputation procedures (Sensitivity Analysis 2).

[figure not shown]

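### The stated power of 96/87/69% needs 150 complete dose-response pairs, but 150 is the number enrolled and nothing is allowed for loss before Week 24; the fixed 0.16 rejection rule also fits only n = 150.

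*Protocol*

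**What the plan says.** **Power.** Protocol 12.4 plans for about 150 enrolled subjects and says "this sample size gives a power of 96% to reject the null hypothesis of no dose-effect correlation if the true correlation is 0.30". It adds 87% at a correlation of 0.25 and 69% at 0.20, all at a two-sided 5% level. SAP 4.3 starts from the same number: "Approximately 150 subjects will be enrolled in order to assess (on the efficacy side) the dose-effect correlation". It notes that the first co-primary endpoint (spleen volume) drives the calculation and that "At the given sample size, power can also be assessed for the second co-primary endpoint" (total symptom score, TSS). Neither section mentions dropout, evaluable subjects or complete pairs.

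**Test.** SAP 7.1 uses the t test for a Pearson correlation on n-2 degrees of freedom, where n "is the sample size of paired observations". Multiple imputation appears only as a sensitivity analysis that may be run.

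**Decision rule.** Protocol 12.2.1 gives the t formula in n and then a cut-off: "With a sample size of 150, the critical correlation that is needed to reject" the null hypothesis is 0.16. The next sentence turns this into a rule without naming n: "If the absolute value of the observed correlation is 0.16 or higher", the null is rejected.

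**Loss so far.** Protocol 4.1.5 reports: "Of the 50 subjects enrolled, 33 (66.0%) subjects completed the Week 24 visit", while "8 (16.0%) discontinued prior to Week 24, and 9 (18.0%) subjects remained on study" with the Week 24 visit still to come.

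**The concern.** The power figures belong to a number of pairs, but the plan attaches them to a number enrolled. The two are equal only if nobody is lost, and the trial's own interim data already show loss.

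The response is the member of the pair that goes missing. SAP 5.9.3.1 defines a final titrated dose for subjects who stop early. Under SAP 5.9.1, however, a spleen scan from an unscheduled visit counts as Week 24 only within Day 141 to 175, and SAP 5.6 sends an unresolved end-of-treatment scan through the same rule. Under SAP 5.9.2.3 and Table 4, the Week 24 TSS is missing if the last diary day falls before Day 161 or if more than 8 of the 28 daily values are missing. TSS pairs may therefore be fewer than spleen pairs.

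Two things are at stake. A reader who relies on the quoted power expects more than the enrolment is likely to deliver, most of all at correlations of 0.20 to 0.25. Under the gatekeeping in SAP 5.4.2, lost power on spleen volume also lowers the chance that the TSS test is confirmatory. In addition, the protocol's fixed cut-off and the SAP's p-value can give different answers on the same data.

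**Working it through.** **Inputs**
- Two-sided alpha 0.05; true correlations 0.30, 0.25 and 0.20; about 150 enrolled (Protocol 12.2.1 and 12.4).
- n is the number of pairs (SAP 7.1).
- At the interim, 33 of 50 had completed Week 24, 8 had discontinued and 9 were pending (Protocol 4.1.5).

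**Formulas**
- Critical correlation: r_c = t / √(t² + n − 2), with t the 97.5% point on n−2 df.
- Power by Fisher's z: Φ{[atanh(ρ) − atanh(r_c)] × √(n − 3)}.

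**Step 1. Reproduce the plan's figures at n = 150.** t = 1.976, so r_c = 1.976/√(1.976² + 148) = 0.160. Its Fisher transform is 0.1617, and √147 = 12.12.
- ρ = 0.30: (0.3095 − 0.1617) × 12.12 = 1.79, power 96.3%
- ρ = 0.25: (0.2554 − 0.1617) × 12.12 = 1.14, power 87.2%
- ρ = 0.20: (0.2027 − 0.1617) × 12.12 = 0.50, power 69.0%

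These match 96/87/69 and 0.16, so the arithmetic is right for 150 complete pairs.

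**Step 2. Expected pairs.**
- Loss of 8/50 = 16%: 0.84 × 150 = 126 pairs. This treats the 9 pending subjects as retained.
- Loss of 8/41 = 19.5%, among those with known status: 33/41 × 150 = 121 pairs.
- Exact 95% confidence interval for 8/50: 7.2% to 29.1%, which is 106 to 139 pairs.

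**Step 3. Power at those numbers.**

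| Pairs | Critical \|r\| | ρ = 0.30 | ρ = 0.25 | ρ = 0.20 |
|---|---|---|---|---|
| 150 (as stated) | 0.160 | 96.3% | 87.2% | 69.0% |
| 139 | 0.167 | 95.0% | 84.6% | 65.7% |
| 126 | 0.175 | 92.9% | 80.8% | 61.3% |
| 121 | 0.179 | 91.9% | 79.2% | 59.5% |
| 106 | 0.191 | 88.1% | 73.6% | 53.8% |

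The exact distribution of r moves these by at most half a percentage point.

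**Step 4. The 0.16 rule at fewer pairs.** With t = 0.16 × √[(n − 2)/(1 − 0.16²)]:
- n = 150: t = 1.972, p = 0.0505
- n = 126: t = 1.805, p = 0.074
- n = 121: t = 1.768, p = 0.080

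An observed correlation between 0.16 and about 0.175 to 0.179 would reject under the protocol's sentence and not under the SAP's p-value. Applied literally at those numbers, 0.16 corresponds to a two-sided error of 7.4% to 8.0%.

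**The case against.** The other side has several fair points.

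- **The calculation is correct for the n it names, and no promise is broken.** Neither document sets a target power, and both call the study exploratory. Power stays above 90% at a correlation of 0.30 with 16% to 20% loss. This limits the seriousness. It does not make a quoted power figure right for a trial that also has formal co-primary tests and a Type I error procedure.
- **Some spleen pairs are recovered.** Subjects who stop before Week 24 have an end-of-treatment scan, and one falling within Day 141 to 175 can serve as the Week 24 value. This stands, but it helps only late discontinuers, whose number the documents do not give. The 16% counts discontinuations, not missing scans.
- **The loss rate is imprecise.** On 8/41 the exact interval is 8.8% to 34.9%, or about 98 to 137 pairs, which is wider than the interval used above. In the other direction, 8/41 may overstate loss, because dropouts become known before completions. Both points argue for stating a range.
- **The 0.16 rule is introduced for n = 150, and the SAP uses the actual n.** That is so, and the planned SAP analysis does not inflate alpha. The decision sentence still names no n and gives no rule for any other number of pairs.
- **The SAP covers Amendment 1, and the interim results appear in the later protocol text.** This explains the gap in SAP 4.3. It does not excuse Protocol 12.4, which sits in the same document as the interim data.
- **No TSS power is stated, and any TSS shortfall is unquantified.** This is correct, so it is given here only as a direction.

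**Conclusion.** The concern holds. The stated power describes 150 complete pairs, and the plan enrols about 150 subjects with no allowance for loss. If loss before Week 24 continues at the interim rate of 16% to 19.5%, power is about 92-93%, 79-81% and 60-61% instead of 96%, 87% and 69%. That is a fall of roughly 3-4, 6-8 and 8-10 percentage points. Over the 95% interval for 8/50 the ranges are 88-95%, 74-85% and 54-66%.

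These figures assume that the interim rate applies to all 150 subjects and that each discontinuation costs one pair. Late scans would raise the spleen number, and diary gaps could lower the TSS number.

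The 0.16 rule is the lesser part. It is a conflict between two written rejection rules, not an inflated error in the SAP analysis. The point should be fixed, but it does not threaten the design.

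**What to change.** 1. **Protocol 12.4 and SAP 4.3:** state power by expected evaluable pairs, as a range. Suggested text: *Power refers to subjects with both a final titrated dose and a Week 24 percent change. If 16% to 20% of 150 enrolled subjects have no Week 24 value, about 121 to 126 pairs are expected, giving power of about 92-93%, 79-81% and 60-61% for true correlations of 0.30, 0.25 and 0.20. Power for TSS may be lower because of the diary-missingness rules.* Add that the loss rate comes from 50 interim subjects and is imprecise.
2. **Protocol 12.2.1:** delete the 0.16 rule or mark it as illustrative for n = 150, and state: *H0 is rejected when the two-sided t-test p-value on n-2 degrees of freedom, with n the number of observed pairs, is below 0.05.*

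The cost is wording and a less favourable stated power. No extra patients, data or analyses are needed. Keeping 150 pairs instead would take about 179 enrolled at 16% loss (150/0.84) or 187 at 19.5% (150 × 41/33), but the correction does not depend on that.
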